#### **4.11. Data Quality Review**

Study database. Data for truthing, readings, and lesion matching on protocol FMSU2017-002A will be provided to BCL following approved data transfer specifications, to be developed by Fujifilm's study data vendor (Prosoft Clinical, Wayne, PA). *Analysis data: Subject level* will be a subset of protocol FMSU2013-004A *Analysis data: Subject level* in the archive generated by BCL for that study. Fujifilm will transfer reader experience data directly to BCL in comma-separated values (CSV) format.

Review and queries. BCL will examine the database for complete data and, if any data points are missing, query Fujifilm regarding reasons for this missingness. BCL also will verify that data values fall in allowable ranges and follow logical flow, and query Fujifilm regarding any exceptions. Fujifilm will resolve any such issues in the database, and provide responses and an updated database to the statistician. BCL will review the replies and updated database, and declare the data "all clean" if BCL determines that all queries have been resolved sufficiently for analysis to proceed. If data are not "all clean", BCL will query any remaining exceptions and Fujifilm will reply as above. Data will be locked only after BCL declares the database all clean.

BCL will use this final study database for all final study analysis. Final study analysis may be delayed until the study database is locked.

Missing Responses, Indeterminate Results, and Outliers. BCL will review the reasons for any missing data to evaluate whether the missingness is most likely missing completely at random,

missing at random, or systematic. BCL will determine appropriate methods for handling the missing data based on this evaluation and the amount of missingness. If BCL needs to amend this SAP to include more details for handling missing data, we will add these details before carrying out the analysis. In particular, if statistical models are used to address missing data issues these models and their assumptions will be explained clearly, and robustness of results will be explored.

The eCRFs are designed to prevent indeterminate responses; if any do occur, BCL will work with Fujifilm to resolve the issue. Regarding outliers the only continuous variable in the dataset is POM, a subjective ordinal variable for which each reader is permitted to use the full range on each case independent of values of other variables, such that no value of POM in 0 – 100% will be categorized as an outlier.

## **5. Results to be Reported**

- *Dates (timeline).*
  - When cases were accrued on protocol FMSU2013-004A.
  - When cases were selected for the reader study.
  - When the readers' interpretations occurred.
  - When lesion matching occurred.
- *Clinical and demographic characteristics of cases.* For example: age, race, ethnicity, breast composition (BI-RADS breast density categories), study center, reference standard status (cancer, benign, recall, normal); and for cancers lesion type (mass, asymmetry, calcification, architectural distortion, other, or combinations thereof) and size (as determined on protocol FMSU2013-004A).
- *Clinical and demographic characteristics of readers.* For example: years in practice, whether the reader had specialized mammography training, number of mammograms read in the past year, percent of current practice that is mammography, usual hours spent in a clinical day (to address issues of reading fatigue), and whether or not they use C-View.
- *Flow diagram.* Reasons for any exclusions (for example, protocol deviations). If exclusions are minimal, this diagram may be omitted and replaced by text.
- *Summaries and cross-tabulations.*

- Table of number of findings by reference standard status and modality for each study reader.
- Means and SDs, and/or medians and quartiles or ranges, of POM requiring correct lesion localization by reference standard status and modality for each study reader.
- Table of BI-RADS requiring correct lesion localization by reference standard status and modality for each study reader.
- Table of recall requiring correct lesion localization by reference standard status and modality for each study reader.
- *AUC (primary endpoint).*
  - Graphs of the readers' non-parametric (trapezoidal) ROC curves based on per-subject POM scores requiring correct lesion localization for each review condition (FFDM read, DBT plus S-View read).
  - Table of corresponding AUCs for FFDM, DBT plus S-View, and the pairwise differences between them.
  - Average across readers of within-modality AUCs and between-modalities differences in AUCs.
  - Two-sided 95% CIs to quantify uncertainty in the within-modality estimates and the between-modalities difference.
  - Corresponding rotated forest plots and/or stacked bar charts (optional).
- *Recall rate for non-cancer cases, specificity, sensitivity, recall rate for cancer cases (secondary endpoints).*
  - Table of readers' estimates for FFDM, DBT plus S-View, and the pairwise differences between them.
  - Average across readers of within-modality estimates and between-modalities differences in between them.
  - Two-sided 95% CIs to quantify uncertainty in the within-modality estimates and the between-modalities difference.
  - Corresponding rotated forest plots and/or stacked bar charts (optional).

- *Performance metrics in important subgroups.*
  - *AUC only:* Graphs of the readers' non-parametric (trapezoidal) ROC curves based on per-subject POM scores requiring correct lesion localization for each review condition (FFDM read, DBT plus S-View read).
  - Table of readers' estimates for FFDM, DBT plus S-View, and the pairwise differences between them.
  - Average across readers of within-modality estimates and between-modalities differences in estimates.
  - Two-sided 95% CIs to quantify uncertainty in the within-modality estimates and the between-modalities difference.
  - *AUC only:* Corresponding rotated forest plots and/or stacked bar charts (optional).
- *Adverse events.* None are expected; any that are reported to BCL will be described.
- *Sample size.*
  - Magnitude and direction of difference between average AUC for DBT plus S-View and average AUC for FFDM.
  - Estimates of variance components and correlations that influence sample sizes and case mix for the pivotal reader study:  $\hat{\sigma}_{ab}^2$  for interaction of reader and modality (DBT plus S-View or FFDM),  $\hat{\sigma}_w^2$  for within-reader variance,  $\hat{\sigma}_c^2$  for variance because cases are a sample,  $\hat{r}_1$  for the correlation between AUCs from the same reader between modalities,  $\hat{r}_2$  for the correlation between AUCs from different readers in the same modality, and  $\hat{r}_3$  for the correlation between AUCs from different readers between modalities.

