	
2. The Truthing Process
 
The truther will review all cancer cases selected for inclusion in the reader study. The truther will complete an eCRF for each case, based on materials from the image acquisition site including mammograms. For each subject with at least one (1) biopsy proven malignant lesion, the truther will review the images and identify, confirm, and annotate lesions including the types of lesions visible within the mammogram and DBT image, the locations of the lesions, and the characteristics of the lesions on the eCRF.
 
3. The Reading Process
 
Approximately 6 qualified radiologists will independently perform two reads on all (approximately 100) cases. Each reader will read each case both as a FFDM read, and a DBT plus S-View read on the ASPIRE Bellus II workstation. Each reader will read half the cases on FFDM and the other half of the cases on DBT plus S-View during one visit. The reader will then read the complimentary FFDM and DBT plus S-View during the second visit. In order to minimize memory recall bias, the two reading visits will be separated by a memory washout period of approximately 4 weeks.
 
Interpretation instructions: The reader will complete the eCRFs for each case for the two reads. For each case on each read, the reader will first record whether there are mammographic findings and an initial BI-RADS assessment of 0, 1, or 2. If the answer to this question is "no" the reader will be asked to confirm for this case: a BI-RADS assessment category of 1 or 2, a POM score following the POM guidance provided in Table 4, and recall decision of "no". If the reader answers "yes" to whether there are mammographic findings, the reader will be asked to confirm an initial BI-RADS assessment category of 0, and will then provide detailed information on each suspicious finding (up to three findings) and the decision whether or not to recall the subject, as well as overall POM score and BI-RADS assessment category.
 
4. The Lesion Matching Process
 
An expert not associated with diagnosing cases at the image-acquisition sites or serving as a reader interpreting images on this pilot reader study will conduct lesion matching. This expert may be an expert mammography technologist with an active license or a board-certified radiologist who is MQSA qualified for both FFDM and tomosynthesis; if a board-certified radiologist who is MQSA qualified for both FFDM and tomosynthesis, this expert may be the same person as the truther.

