### **3.3. Image Review Procedures**

Study readings will occur at International HealthCare, LLC (Norwalk, CT) between 4 November 2017 and 9 December 2017. Each reader will read both FFDM and DBT plus S-View images for each case, separated by a memory washout period, on the ASPIRE Bellus II workstation.

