#### **4.7. Test Reproducibility**

Test reproducibility will not be evaluated on this pilot MRMC study.

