#### **4.10. Sample Size Calculations (Obtaining Parameters)**

Parameters to use in sample size calculations for the pivotal study will be obtained from analysis of AUCs. The magnitude and direction of differences between AUCs the DBT plus S-View read compared with the FFDM read, and variance components and correlations that influence sample sizes for the pivotal reader study comparing them, will be obtained from MRMC analysis. In particular, we will obtain estimates of average AUC within each modality,

$\sigma^2_b$ ,  $\sigma^2_{ab}$ ,  $r_1$ ,  $r_2$ ,  $r_3$  (all defined below), and  $r_b$ , the correlation between the set of AUCs in the two (2) modalities.

Modeling Framework: Let  $A_{ij}$  be an estimate of the AUC in modality  $i$  ( $i = 1$  for FFDM, 2 for DBT plus S-View) for the  $j^{\text{th}}$  radiologist ( $j = \text{reader 1, ..., } J$  for  $J = 6$ ). We consider the effects of radiologists to be random, because interest extends beyond the radiologists on this study to a larger population of potential radiologists from which these radiologists are a sample.

Obuchowski and Rockette model these estimates using mixed effects ANOVA, as

$$A_{ij} = \mu + \alpha_i + b_j + (ab)_{ij} + e_{ij}$$

where

- $\mu$  is the overall AUC across the populations of readers and cases,
- $\alpha_i$  is the fixed effect of modality,
- $b_j$  is a random effect for reader with expectation 0 and variance  $\sigma^2_b$  with random effects for different readers independent of each other,
- $(ab)_{ij}$  is a random effect for the interaction of modality and reader with expectation 0 and variance  $\sigma^2_{ab}$  also with random effects for different readers independent of each other, and
- $e_{ij}$  is random error with expectation 0, variance  $\sigma^2_c + \sigma^2_w$ , and covariance
  - $r_1 \sigma^2_c$  for two AUCs from the same reader in different modalities,
  - $r_2 \sigma^2_c$  for two AUCs from different readers in the same modality, and
  - $r_3 \sigma^2_c$  for two AUCs from different readers in different modalities.

The variance components  $\sigma^2_c$  and  $\sigma^2_w$  are case sample variance and within-reader variance, respectively.

- The random effects  $b_j$ ,  $(ab)_{ij}$ , and  $e_{ij}$  are independent of each other.
- When the readers review the case sample only once in each modality  $(ab)_{ij}$  and  $e_{ij}$  are not identifiable, and we cannot separate  $\sigma^2_{ab}$  from  $\sigma^2_c + \sigma^2_w$ .

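### SAP Section 5 promises separate within-reader and case-sample variances, but one read per modality identifies only their sum, so the split used for pivotal planning must be an assumption

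*SAP*

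**What the plan says.** Protocol 7.1 names variance components and correlations among the things the pilot must deliver for the pivotal study, and SAP Section 1 gives the same planning purpose.

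SAP 4.10 sets up the model. The error in an estimated AUC has variance σ²_c + σ²_w, and these two terms "are case sample variance and within-reader variance, respectively". The three error covariances are r1σ²_c (same reader, different modality), r2σ²_c (different readers, same modality) and r3σ²_c (different readers, different modalities). The variance of the difference in average AUC with J readers is (2/J){σ²_ab + σ²_w + σ²_c[1 − r1 + (J−1)(r2 − r3)]}. Pilot data are to supply its components and correlations. Case numbers enter through σ²_c, for which 4.10 cites a binormal closed form. A caveat says that with a single review per modality σ²_ab cannot be separated from σ²_c + σ²_w.

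SAP Section 5 then lists as results an estimate "for within-reader variance", another "for variance because cases are a sample", and r1 to r3, describing r1 as "for the correlation between AUCs from the same reader between modalities".

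On the reading design, the Protocol synopsis says the readers "will independently perform two reads on all (approximately 100) cases", one per modality. SAP 3.3 agrees: "Each reader will read both FFDM and DBT plus S-View images for each case". SAP 4.7 adds: "Test reproducibility will not be evaluated on this pilot MRMC study".

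**The concern.** Separating a reader's own inconsistency from case sampling needs the same reader to read the same cases in the same modality more than once. This design has no such replicate, so Section 5 names an estimate that the pilot cannot give. Because 4.10 scales the covariances on σ²_c and not on the total error variance, r1 to r3 inherit the problem. The caveat in 4.10 covers a different pair of quantities and does not mention this one.

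What is at stake is pivotal planning. Under 4.10, more cases reduce σ²_c and leave σ²_w where it is. The share given to σ²_w therefore decides how much precision the extra cases appear to buy.

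**Working it through.** **Inputs from the documents.** J = 6 readers (SAP 2), 18 cancer and 82 non-cancer cases (SAP 2.1), one read per reader, case and modality, and the model and formula of SAP 4.10. The documents give no variance or correlation values, so every such value below is an assumption.

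**Step 1: count.** Case-level data yield four error quantities: σ²_e = σ²_c + σ²_w, Cov1, Cov2 and Cov3. The model has five unknowns: σ²_c, σ²_w, r1, r2 and r3. One is left free.

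**Step 2: same data, different answers.** Take σ²_e = 0.0025, Cov1 to Cov3 = 0.0012, 0.0010, 0.0008, σ²_ab = 0.0002 and J = 6. Let w = σ²_w/σ²_e. The error part is the σ²_w and σ²_c terms of the formula.

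| w | σ²_c | σ²_w | r1, r2, r3 | Error part |
|---|---|---|---|---|
| 0 | 0.0025 | 0 | 0.48, 0.40, 0.32 | 0.0025 × 0.92 = 0.0023 |
| 0.2 | 0.0020 | 0.0005 | 0.60, 0.50, 0.40 | 0.0005 + 0.0020 × 0.90 = 0.0023 |
| 0.5 | 0.00125 | 0.00125 | 0.96, 0.80, 0.64 | 0.00125 + 0.00125 × 0.84 = 0.0023 |

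Every row gives var = (2/6)(0.0002 + 0.0023) = 0.00083333. The full 12 × 12 covariance matrix of the AUCs is the same for each split, and computing the variance directly from it also gives 0.00083333, so the SAP formula is algebraically correct.

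**Step 3: limits on w.** No r can exceed 1, so w cannot exceed 1 − max(Cov)/σ²_e. The split is bounded but not determined.

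**Step 4: can the binormal value isolate σ²_c?** A simulation used 18/82 cases, an assumed AUC of 0.85, normally distributed ratings with reading noise independent across cases, and 8,000 runs per setting. True within-reader variance rose from 0 to 0.00161 and true case variance fell from 0.00239 to 0.00082. The one-read DeLong estimate stayed at 0.00245 to 0.00246. The equal-variance binormal value is 0.00242. In that setting both track the sum.

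**Step 5: effect when case numbers change.** Write ρ1 to ρ3 for Cov1 to Cov3 divided by σ²_e, and D = 1 − ρ1 + (J−1)(ρ2 − ρ3). With m times the cases and σ²_w held fixed, as 4.10 implies, each SAP correlation is ρ/(1−w) and

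var = (2/J){σ²_ab + (σ²_e/m)[D + (m−1)w]}.

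At m = 1, w drops out. Assume J = 12, m = 3, σ²_e = 0.0025 at pilot size, σ²_ab = 0.0002, ρ = 0.5, 0.4, 0.3, margin 0.05 (the pilot margin in SAP 4.6.1, carried over) and true difference 0. Then D = 1 − 0.5 + 11 × 0.1 = 1.6, and power = Φ(0.05/SE − 1.96).

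| w | D + 2w | var | SE | Power |
|---|---|---|---|---|
| 0 | 1.6 | 0.000256 | 0.0160 | 87.9% |
| 0.1 | 1.8 | 0.000283 | 0.0168 | 84.4% |
| 0.3 | 2.2 | 0.000339 | 0.0184 | 77.5% |

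Here w = 0.5 is the limit from Step 3, where r1 equals 0.5/0.5 = 1.

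With the Step 2 covariances, D = 1 − 0.48 + 11 × 0.08 = 1.4. The variances are 0.000228, 0.000256 and 0.000311, and power is 91.2%, 87.9% and 80.9%, for the same three shares. Relative to w = 0, variance rises by 11% to 12% at w = 0.1 and by 33% to 37% at w = 0.3 across the two sets.

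If σ²_w also shrinks with the case number, the variance stays at its w = 0 value for every split.

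**The case against.** The strongest reply has four parts.

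- **The 4.10 caveat already treats σ²_c + σ²_w as one sum.** It does, but only to say that σ²_ab cannot be separated from it. It does not say that the two terms are inseparable from each other, and Section 5 then lists both.
- **The binormal expression supplies σ²_c, leaving σ²_w as the remainder.** SAP 4.10 does assign that expression to σ²_c. This is a modelling choice, and in Step 4 the value matched the sum, so the remainder would not be a valid estimate of within-reader variance.
- **The cited method papers may contain a single-read convention.** That cannot be checked here. The point is limited to what the SAP itself says.
- **The split cancels at a fixed case count, the pivotal study has its own protocol, and the pilot is not intended as a basis for approval.** All of this stands and sets the scope.

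Some stronger readings are tempting but unsupported. A reader might infer that the SAP is silent on how the error scales with case number; it is not, since case numbers act only through σ²_c. A reader might expect σ²_w to be counted twice, but no passage describes such a procedure. Nor do the documents support pooling all error and letting it all shrink with cases as the default, because that is the optimistic end of the range.

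**Conclusion.** The point holds in limited form. With one read per modality, SAP Section 5 cannot deliver separate estimates of σ²_w and σ²_c, and r1 to r3 on the σ²_c base of SAP 4.10 are not point-identified. What can be estimated is σ²_e, the three covariances and the correlations scaled on σ²_e.

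A reader might infer that the pilot's AUC comparison or its confidence interval is compromised. It is not: the variance of the difference at pilot case numbers is the same for every split.

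The consequence is confined to pivotal planning, and its size cannot be fixed from the documents. Under the main set of assumptions, a non-shrinking share of 30% instead of 0% takes power from 87.9% to 77.5%. A 50% share is the limiting case there and should not be read as an ordinary scenario. If all reading noise shrinks with cases, there is no effect. The text still needs correcting, because supplying these components is the pilot's stated purpose.

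**What to change.** - **SAP Section 5:** replace the separate σ²_w and σ²_c estimates with σ²_e, Cov1 to Cov3, and correlations defined as each covariance divided by σ²_e.
- **SAP 4.10, modelling framework:** add that σ²_c and σ²_w cannot be separated with one read per modality.
- **SAP 4.10, sample size framework:** keep the formula, but label σ²_w as an assumed share w of σ²_e and not a pilot estimate. For each w, recompute r1 to r3 as the covariance divided by (1−w)σ²_e. Report pivotal variance and power for w from 0 up to at most 1 − max(Cov)/σ²_e. State that w = 0, where all error scales with cases, is the optimistic end. State how the binormal value is reconciled with the assumed w.
- **Optional:** align the two parameter lists. SAP 4.10 names σ²_b and r_b ("the correlation between the set of AUCs in the two (2) modalities"), which its fallback for a negative σ²_ab estimate needs, and Section 5 omits them. Also reconcile the σ²_ab caveat with the unbiased ANOVA estimate mentioned later in 4.10; that estimate is available once the error covariances come from case-level data.

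The cost is SAP text only, with no new reads or data. The downside is that σ²_w is no longer reported as an estimate and pivotal planning shows a range in place of a single value.

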## **6. Regulatory and Administrative Information**

If requested, BCL will provide an electronic copy of line data and associated metadata to Fujifilm. Also upon request, BCL will provide an electronic copy of statistical software code and/or its output for use in regulatory review, under the conditions of the contract between BCL and Fujifilm.

Analyses will be performed using R version 3.4.1 or later (2017-06-30; R Foundation for Statistical Computing, <https://www.R-project.org>) and cross-validated by standard BCL quality control methods.

**Appendix 1**  
**Case Report Forms (CRFs)**

(CRFs follow)

### **RADIOLOGIST READER QUESTIONNAIRE**

Protocol Number(s):	FMSU2017-002A
1. Name:	
2. How many years have you been reading mammograms?	
3. In your most recent MQSA report, how many cases did you review in a year?	
4. How many hours do you read in an average clinic day?	
5. How many years have you been reading FFDM images?	
6. How many months/years have you been reading DBT images?	
6a. What DBT manufacturer do you regularly use?	
6b. What percentage of mammography cases do you perform with DBT?	
6c. If not 100%, what criteria do you use to decide which patients are imaged with DBT?	
6d. Do you use synthetic 2D with DBT?	
6e. If so, what percentage of mammography cases do you use synthetic 2D for?	
7. With respect to this reader study, what changes to the training program would you suggest?	
8. Please describe your overall impression of the reader study.	
9. Please describe any changes you would suggest to the overall reader study.	

FMSU2017-002 \_Reader Questionnaire\_20171031

**BIOSTATISTICS CONSULTING, LLC**

---

---

10. Please describe your overall impression of the image quality of the FFDM mammograms.	
10a. Please describe any changes you would suggest to the image quality of the FFDM mammograms.	
11. Please describe your overall impression of the image quality of the DBT images.	
11a. Please describe any changes you would suggest to the image quality of the DBT images.	
12. Please describe your overall impression of the image quality of the S-View images.	
12a. Please describe any changes you would suggest to the image quality of the S-View images.	
13. Please describe your overall impression of the Bellus II Workstation?	
14. Please describe any changes you would suggest to the Bellus II Workstation?	
15. Please describe your overall impression of the travel arrangements/accommodations.	
16. Any additional comments:	

FMSU2017-002 \_Reader Questionnaire\_20171031

# BIOSTATISTICS CONSULTING, LLC

---

FUJIFILM Medical Systems U.S.A., Inc.

PROTOCOL: FMSU2013-004A EDMS No.: IQG-0031788-D	Subject ID #: 
 
			
 
 - 
 
			
 
							Subject Initials (F/M/L): 
 
			
 
			

## SUBJECT DEMOGRAPHICS AND INCLUSION/EXCLUSION CRITERIA

1. Date of Consent (mm/dd/yy): 

--	--	--

 - 

--	--	--

 - 

--	--	--
2. Age of Subject: 

--
3. Date of Birth (mm/dd/yy): 

--	--	--

 - 

--	--	--

 - 

--	--	--
4. Ethnicity:  Hispanic or Latino  Not Hispanic or Latino  Unknown/Not Reported
5. Race:  American Indian or Alaska Native  Black or African American  Asian  
 Native Hawaiian or other Pacific Islander  White  Other: \_\_\_\_\_
6. Subject enrolled as (check one):  Screening  Diagnostic  Recall

7. Inclusion Criteria: (Subject may not be enrolled if any criteria are answered as "no")

	Yes	No	N/A
a) For the screening-group subjects, is the subject at least 40 years of age, asymptomatic, and scheduled for a routine screening mammogram?			
b) For the diagnostic-group subjects, is the subject at least 18 years of age; Scheduled for a biopsy due to an assessment of BI-RADS® 4 or 5 after diagnostic work-up of a suspicious screening or clinical finding within the last 60 days.			
c) For the recall-group subjects, is the subject at least 18 years of age; Received a BI-RADS 0 within the last 60 days, and are recalled for additional imaging.			
d) Have the ability to understand the requirements of the study, to provide written informed consent, and to comply with the study protocol			
e) Meet none of the exclusion criteria			

8. Exclusion Criteria: (Subject may not be enrolled if any criteria are answered as "yes")

	Yes	No
a) Presence of an implant		
b) Women with only a single breast; for example, post mastectomy patients.		
c) Is pregnant or believes she may be pregnant.		
d) A woman who has delivered and who has expressed the intention to breast-feed or is currently breast-feeding.		
e) A woman who has significant existing breast trauma within the last one (1) year.		
f) Has self-reported severe non-focal or bilateral breast pain affecting subject's ability to tolerate digital mammography and/or breast tomosynthesis examinations.		
g) A woman who has had a mammogram performed for the purpose of therapy portal planning within the last one (1) year.		
h) Cannot, for any known reason, undergo follow-up digital mammography and/or breast tomosynthesis examinations (where clinically indicated) at the participating institution.		
i) Is an inmate (see US Code of Federal Regulations 45CFR46.306)		

